
	1. change in Everyday Cognition (score range: 1 to 4)		
	2. change in Geriatric Depression Scale score (score range: 0 to		
	15)		
	3. change in Pittsburgh Sleep Quality Index global score (score		
	range: 0 to 21)		
	4. change in EuroQol EQ-D5 utility score (score range: -1 to 1)		
Covariates	There are no pre-specified covariates for the primary and secondary		
	endpoints.		
Follow-up schedule	16 weeks (mid point), 24 weeks (intervention termination), 48 weeks		
,	(post-intervention follow-up)		
Masking	Outcome assessors, data analysts		
Number of subjects	The target sample size is 315 participants to provide 80% power to		
3	detect a medium-size difference in mean MoCA change of 1.5 points		
	between the cognitively enhanced tai ji quan and the standard tai ji		
	quan groups and a large-size difference of 3 points between the		
	cognitively enhanced tai ji quan and the stretching control groups at 24		
	weeks.		
Statistical analysis	The effect of the intervention on the primary endpoints will be		
	evaluated using the intention-to-treat approach, in which participants		
	are grouped according to randomization assignment. To compare		
	change in outcome measures among the three intervention groups at 6		
	months, we will analyze a 3 (Group) by 3 (Time) mixed-effects model		
	with repeated measures on the second factor (i.e., outcome measures		
	assessed at baseline, 4 months, and 6 months). In the presence of a		
	Group by Time interaction effect, pre-specified follow-up pair-wise		
	comparisons will be performed to determine between-group		
	differences (indicated below). Secondary outcomes will be similarly		
	analyzed. Results from primary analyses will be presented as the		
	difference in mean MoCA and dual-task performance between the		
	cognitively enhanced tai ji quan and standard tai ji quan groups and		
	between the cognitively enhanced tai ji quan and the stretching		
	exercise control, with a Bonferroni-adjusted 2-tailed significance level		
	of .0125 for each of the two primary outcomes and a 98.75%		
Intonia analysis	confidence interval.		
Interim analysis	No interim analyses for efficacy or futility. However, interim		
	monitoring is performed with a focus on subject accrual, intervention		
	fidelity, protocol adherence, data completeness and quality, and		
	intervention safety and analysis.		

Study Background and Rationale

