The primary measures of global cognitive function and dual-task gait performance ability and other specified secondary and tertiary outcome measures will be assessed at baseline (before randomization), 4 months (midpoint), and 6 months (intervention termination). The repeated data collection will be performed by outcome assessors who have gone through a training process to familiarize themselves with the assessment protocol. All assessors will be blinded to group allocation.

Primary endpoints

Primary efficacy endpoints for the trial are changes in global cognitive function and cost of dual-task gait performance at 6 months from baseline.

Global cognitive function will be assessed by the Montreal Cognitive Assessment (MoCA),²¹ which measures cognitive function of multiple domains (attention/concentration, executive functions, short-term memory, language, visuospatial abilities, orientation to time and place). The MoCA will be administered to the study participants by trained study assessors at baseline, 4 months, and 6 months. MoCA has a total score that ranges from 0 to 30, with higher scores representing better cognitive functioning. One point is added to the total scores for participants who received less than 12 years of education. To avoid potential practice effect associated with the repeated measures, we will use a different version at each of the three assessment time points (Note: Version 8.1 at baseline, Version 8.2 at 4 months, Version 8.3 at 6 months [Version 8.1 is repeated at 12 months]).

Dual-task cost will be assessed via an Instrumental Timed Up&Go (*i*TUG) gait performance (APDM, Inc.) in which the participant is asked to stand up from a chair, walk a 6-m walkway at normal pace (3 m toward a line, turn, and 3 m toward the chair), turn around, and sit down on the chair, with no cognitive task (single-task walking). The participant is then asked to perform the same procedure with a concurrent cognitive task (counting backward by 3s, starting with an odd number, e.g., 81).¹² The total walking duration (in seconds) during both 6-meter walks, at normal pace, will be recorded. These tests will be administered by trained study assessors at baseline, 4 months, and 6 months. Using the score ascertained from each walk, a dual-task cost measure is estimated using the following formula:

- (1) Dual-task walking cost_{baseline} = (dual-task walking single-task walking) / single-task walking x 100

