 - Participants' characteristics ascertained at baseline will be compared across intervention groups using independent samples or Wilcoxon rank sum tests, as appropriate, for continuous variables and a chi-square or Fisher's exact tests, as appropriate, for categorical variables. Although no significant differences are expected due to the randomized intervention assignment and the relatively large sample size, any variables found to be significantly different will be noted and accounted for, by controlling for them as covariates in supplements to the main analyses.
- *Time-specific and change scores*. Scores at each follow-up and change in mean scores from baseline at 24 weeks, by intervention group, for all outcome measures will be calculated and presented.
- *Intervention adherence, attrition, and retention*. Class attendance data will be calculated as the average number of scheduled intervention sessions (48 total) attended by participants across intervention groups. Study attrition and retention rates will also be calculated and reported, by intervention group, as the number of participants who completed the 24-week intervention and those who completed all scheduled study follow-up assessments.

Analysis populations

Efficacy analyses. The effect of intervention on the co-primary study outcomes will be evaluated using an intention-to-treat approach in which participants will be analyzed according to randomization assignment. A modified intention-to-treat analysis will be conducted that includes all participants who have undergone randomization and have completed all study follow-up assessments, regardless of their participation adherence status. Finally, a per-protocol analysis will include participants in the intention-to-treat population who have an overall class attendance rate of $\geq 75\%$ (out of the total planned 48 intervention class sessions) of their assigned exercise intervention.¹⁰

Co-primary endpoint analyses

To test the *Primary hypothesis*, we plan to use a generalized linear mixed model with random intercepts and fixed treatment effects for the primary outcomes. Specifically, we will determine the intervention effect through an analysis of a 3 (Group) by 3 (Time) mixed-effects model with repeated measures (follow-up time point) on the second factor (i.e., outcome measures assessed at baseline, 4 months [mid-point], and 6 months [intervention termination]).

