Intervention fidelity will focus primarily on issues such as (a) interventionist qualifications and training, (b) teaching quality of the individual forms/movements or routine in each session, (c) exercise intensity and consistency in training dosage across different sites, and (d) weekly class attendance checking and monitoring. The evaluation will be conducted monthly by either an authorized research team member or an instructor, per guidelines specified in an established fidelity checklist. ¹⁰ In evaluating the item in (b), high intervention fidelity will be considered achieved if at least 95% of the mandatory components (overall completion of pre-specified activities, quality of verbal and visual instructions, emphasis of core training points, session completion time) are fully or partially delivered in each session. Deviations related to intervention delivery protocol will be captured on a protocol deviation form and be entered into a project database for evaluation by the research staff and Principal Investigator. Prompt action will be taken by the Principal Investigator to remedy any problems and deviations identified.

Data completeness and quality control

Data completion refers to the study measurement ascertainment status from all enrolled study participants. The project strives to collect study outcome measures on every participant at each scheduled time point (baseline, 4 months, 6 months, and 12 months), regardless of his/her intervention participation status. As specified in the protocol for the study, we have planned an overall study retention rate of 85% (i.e., having primary and secondary outcome measures available on 85% of the enrolled participants and their informants). To accomplish this goal, planned measures will be taken to ensure that as many participants as possible, including dropouts, attend each scheduled in-person assessment visit at our research facilities. Our proactive methods will include frequent telephone and e-mail contacts with subjects who miss scheduled data assessment appointments. The planned completion of data ascertainment at each follow-up time point is described in the Table 2 below.

Table 2. Projected completion of data ascertainment on study outcome measures at each measurement time point

Measure\Time point	4 months	6 months	12 months
Primary	95%	90%	85%
Secondary	95%	90%	85%
Tertiary	95%	90%	85%

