All data collected (self-reports, interviews, recorded study outcome performance ratings or scores) from the project will first be stored in locked filing cabinets in a designated area inside the ORI office building and, after review for completeness and accuracy, will be entered into a secure, password-protected ORI computer network database to be established by the data team staff. Only authorized project staff conducting this project will have full access to the data collected. Participants and informants' responses to the project surveys, interviews, and other forms of data will be coded with a unique numeric identification code. Only designated project staff will have the key to the file cabinets or password to the database and will have access to the data only for status checking or data verification purposes. An Excel data system will be created to track the subjects' status related to recruitment, enrollment, intervention participation, and follow-up assessment. For all raw data, a system file will be created, using the SPSS statistical software, that merges various subsets of data for final analyses. A periodic security check on the data files will be conducted under the supervision of project's statistician. Only the designated data analyst, project biostatistician, and PI will have access to the raw data and analyses.

Timing of Statistical Analysis

To address the primary aim of the study, preliminary and main statistical analyses and evaluation of the trial primary and secondary outcome measures specified in this protocol will begin immediately upon completing the last study participant follow-up at 6 months. To address the secondary aim of the study, analyses and evaluation of trial data will begin immediately upon completing the last study participant follow-up at 12 months.

Adverse Events Reporting

The following summarizes the procedures that will be followed by the investigative team when a participant experiences an adverse event (during the entire course of the study project):

- 1. The participant will be encouraged to call ORI's research staff at [contact] or [contact] (toll free).
- 2. ORI's staff will file an incident report and immediately report the event to the Principal Investigator ([name].).
- 3. The Principal Investigator will inform ORI's IRB administrator ([contact]) and project Safety Officer appointed by NIA of the incident within 48 hours.

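### Read literally, the supplementary modified intention-to-treat set is a completer set that depends on the 48-week visit, which comes after the 24-week primary endpoint

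*Protocol*

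**What the plan says.** The definition is in the Protocol's statistical analysis plan under Analysis populations, and the separate SAP repeats it word for word. After the intention-to-treat analysis, a modified version is planned that "includes all participants who have undergone randomization and have completed all study follow-up assessments, regardless of their participation adherence status". The rule does not name the visits. Other parts of the documents bear on what it covers:

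- **Follow-up schedule.** The Protocol synopsis lists "16 weeks (mid point), 24 weeks (intervention termination), 48 weeks". Table 1 gives 4, 6 and 12 months for every outcome. Data completeness and quality control refers to "each scheduled time point (baseline, 4 months, 6 months, and 12 months").
- **A narrower schedule.** The Protocol's Assessment schedule paragraph says that the outcomes "will be assessed at baseline (before randomization), 4 months (midpoint), and 6 months (intervention termination").
- **Primary endpoint and model.** The endpoints are "changes in global cognitive function and cost of dual-task gait performance at 6 months from baseline". The model under Co-primary endpoint analyses uses baseline, 4 months and 6 months.
- **Timing.** Under Timing of Statistical Analysis, the primary-aim work "will begin immediately upon completing the last study participant follow-up at 6 months". The secondary-aim work starts after the last 12-month visit.
- **Retention.** The text says "we have planned an overall study retention rate of 85"%. Table 2 projects 95%, 90% and 85% completion at 4, 6 and 12 months.
- **Missing data.** The primary analysis follows randomised assignment, with ten multiple imputations.

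**The concern.** A set labelled modified intention-to-treat is normally taken to stay close to everyone randomised. This one does not. Its clause on adherence rules out selection by class attendance, but selection by visit completion remains. If the 48-week visit counts, two things follow for the 24-week endpoints.

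First, membership depends on something that happens up to 24 weeks after the endpoint is measured. A participant with complete data for the primary model leaves the set because of a visit outside that model. If later drop-out is related to earlier response, and differs by arm, the comparison is no longer between the groups as randomised.

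Second, the set is not known on the date when the primary-aim analysis is due to start. Anyone applying the rule has to wait for the 12-month data.

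What is at stake is how far a reader can rely on this supplementary analysis as a check on the primary result.

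**Working it through.** **1. Does the rule reach 48 weeks?** The synopsis, Table 1 and the data-completeness section all include the 48-week or 12-month visit. The Descriptive analyses section also reports two separate counts: "the number of participants who completed the 24-week intervention and those who completed all scheduled study follow-up assessments". The plan therefore does not treat finishing the 24-week programme as the same thing as finishing all follow-up. Only the Assessment schedule paragraph stops at 6 months, and the MoCA description that follows it assigns a test version to 12 months. The literal reading includes 48 weeks.

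**2. The plan's own total.** Power estimation gives 267 evaluable participants and 15% loss: 267 / 0.85 = 314.1, rounded up to 315. This reproduces.

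**3. Size of the set, from Table 2 with N = 315.**

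- With 24-week data: 315 × 0.90 = 283.5.
- Monotone dropout (no one returns after a missed visit): the set is 315 × 0.85 = 267.75. Excluded despite having 24-week data: 283.5 − 267.75 = 15.75, about 16 people, or 15.75 / 283.5 = 5.6% of those with the endpoint. All are excluded for the 48-week visit alone.
- Independent missed visits: 0.95 × 0.90 × 0.85 = 0.727, so the set is about 228.9. Excluded despite having 24-week data: 283.5 − 228.9 = 54.6, about 55 people. Some of these missed the 4-month visit.
- Missed visits that never overlap: 1 − (0.05 + 0.10 + 0.15) = 0.70, so the set is 220.5, the smallest that Table 2 allows.

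**4. Sensitivity to the other planning figure.** Power estimation assumes 15% loss by 6 months. Then 315 × 0.85 = 267.75 people have 24-week data. With 85% retained at 12 months, the monotone set is also 267.75, and no one is excluded for the later visit.

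**5. Timing.** Subject accrual plans ten waves over 3.5 years (42 months). Assuming even spacing, waves are 42/10 = 4.2 to 42/9 = 4.7 months apart. When the last wave reaches 24 weeks (about 5.5 months), the wave before it is at about 9.7 to 10.2 months, short of 48 weeks (about 11.0 months). Two waves, 2 × 31.5 = 63 to 2 × 35 = 70 people, would have no 48-week status. Under any spacing, at least the last wave has none.

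**6. Precision.** For 1.5 MoCA points, SD of change 3.5 and two-sided 0.05 (the level used in the plan's power section), power is 83.8% at 90% completion (94.5 per arm) and 81.7% at 85% (89.25 per arm). Loss of precision is not the issue.

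**The case against.** The strongest reply is that 48 weeks is an inference. The sentence names no visits, it sits in a paragraph about 24-week outcomes, and one schedule paragraph ends at 6 months. The authors may have meant follow-up through 24 weeks. That stands as a possibility, but it is not written, and most of the scheduling text points the other way. Even on that reading the set is a completer set, and the label does not say so.

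Three stronger conclusions are tempting and are not supported.

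- *That the set was chosen after results were seen.* The rule is pre-specified in both documents. Only each person's membership depends on a later event.
- *That the set must be redefined to be used at all.* The timing section says when primary-aim work begins, not when every supplementary analysis must be finished. A second analysis point follows the last 12-month visit, and the set can be formed then exactly as written. The consequence is delay.
- *That a bias in MoCA points can be quoted.* Removing the worst-responding 15% of one arm and none of the other would shift that arm's mean by 0.233 / 0.85 × 3.5 = 0.96 points. The same formula with the 5.6% from Table 2 gives about 0.42. Equal selection in both arms gives zero. The documents give no arm-specific loss and no link between response and drop-out, so none of these figures can be preferred. The 15% also includes people with no 24-week value, who would be missing from a 24-week completer set too.

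It is also fair to say that the plan gives this set no confirmatory role, states its composition openly and reports retention by arm.

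**Conclusion.** The concern holds as a minor one about a supplementary analysis. Taken literally, the modified intention-to-treat set is a completer set that requires the 48-week visit. It excludes people with an observed 24-week endpoint and cannot be formed until the 12-month follow-up is complete.

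About 16 of 315 are affected if Table 2 holds and dropout is monotone. The number is higher if missed visits are scattered (about 55 under independence, including some who missed only the 4-month visit). It could be near zero if the 15% loss by 6 months is the better projection. The documents do not reconcile these two projections.

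The primary intention-to-treat analysis with multiple imputation keeps every observed 24-week value and can run on schedule, so a reader should not infer that the main result is compromised. The size and direction of any bias in the supplementary analysis are unknown.

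**What to change.** For the 24-week endpoints, replace the set with all randomised participants with available outcome data, analysed as randomised by the planned mixed model without imputation. The plan already contains the pieces: its missing-data section refers to running the same model on non-imputed data, and its CDR-SB growth model uses all available data and is described as intent-to-treat.

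Alternatively, keep a complete-case set, define it by the visits through 24 weeks, and call it a completer analysis. In either case, keep any set that requires the 48-week visit for the 12-month durability analysis.

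The cost is a change of SAP wording and one re-defined supplementary analysis. The replacement does not remove selection altogether, because it still conditions on having post-baseline data, but it no longer discards endpoint values that were observed.

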In the presence of a Group by Time interaction effect, follow-up pair-wise comparisons, using independent t tests, will be performed to identify a priori specified between-group differences. Specifically, we will determine the intervention effect of cognitively enhanced tai ji quan for change in MoCA and costs of dual task in gait performance from baseline to 24 weeks by making a comparison between cognitively enhanced tai ji quan and standard tai ji quan and between cognitively enhanced tai ji quan and stretching exercise.

Level of statistical significance and confidence intervals. Our primary outcome analyses will be 2-sided with an adjusted significance level of <0.0125 (0.05 / 4 comparisons) and a 98.75% confidence interval (CI). For each group, both estimated means and their corresponding standard error of estimates at each assessment point will be presented. In presenting between-group differences, mean differences with CIs will be presented. SPSS "MIXED" function will be used in analyzing our primary outcomes.

Secondary and tertiary outcome analyses

A similar analytic approach will also be applied to all secondary and tertiary (continuous) outcome variables described in Table 1. All study outcomes are expected to follow a normal distribution. In the case of deviation from normality, generalized estimating equations will be used to assess the effect of intervention over time. No Bonferroni correction will be made to account for multiple comparisons.

Level of statistical significance and confidence intervals. All tests and CIs will be 2-sided, and statistical significance will be defined as a P value of <0.05. For each group, we will report both estimated means and their corresponding standard error of estimates at each assessment point. In presenting between-group differences at 24 weeks, estimated mean differences with CIs will be presented.

Analyses on examining intervention durability at 48-week follow-up

We will use the same analytic strategy outlined in our primary and secondary outcome analyses, with the exception of CDR-SB (described in detail below), to examine whether the intervention effects will persist 24 weeks after the end of the 24-week supervised interventions (*Secondary hypothesis*).

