With the longitudinal data, we will test the hypothesis that the rate of improvement over time in the mean CDR-SB score, at 24-week post-intervention follow-up, will be greater in the cognitively enhanced tai ji quan group compared with the other two exercise groups. To test this hypothesis, we will use the latent growth curve modeling approach,³⁵ with maximum-likelihood estimation, analyzing the rate of change in the mean CDR-SB score defined by the four measurement time points: baseline, 16 weeks (mid intervention assessment), 24 weeks (end of intervention assessment), and 48 weeks (24 weeks post intervention follow-up).

Accordingly, we will operationalize our basic growth curve model with two latent growth factors: Intercept (defining the initial level of CDR-SB – baseline) and Slope (defining the rate of change over the course of the 48-week study period), with each factor being defined by the four time-specific CDR-SB

measures. A schematic representation of the planned latent growth model to be evaluated for each intervention group is shown in Figure 1. The factor loadings for the Intercept factor will be fixed with a constant value of 1 for all measurement points whereas the loadings for the Slope factor, defining the rate of change over time, will be fixed at 0 for CDR-SB at baseline, 1 for CDR-SB at 16 weeks, 2 for CDR-SB at 24 weeks, and * for CDR-SB at 48 weeks (where * indicating an undefined, free estimate at 48 weeks). All other model parameters to be estimated include latent Intercept mean and its variance, latent Slope mean and its variance, the correlation between Intercept and Slope (covariance), and error variance for each of the four time-specific measurements (shown as E's). The model estimation will include all available data derived from the trial, hence, an intent-to-treat approach.

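### The primary mixed model names random intercepts but no residual covariance, and the plan does not say where the standard error of the 24-week contrasts comes from

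*Protocol*

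**What the plan says.** The Co-primary endpoint analyses section has the same text in the Protocol and the SAP. It plans a "generalized linear mixed model with random intercepts and fixed treatment effects for the primary outcomes", then describes a 3 (Group) by 3 (Time) "mixed-effects model with repeated measures (follow-up time point) on the second factor", with "outcome measures assessed at baseline, 4 months [mid-point], and 6 months [intervention termination". The section on durability at 48 weeks gives the visit weeks: "baseline, 16 weeks (mid intervention assessment), 24 weeks (end of intervention assessment), and 48 weeks".

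If there is a Group by Time interaction, "follow-up pair-wise comparisons, using independent t tests, will be performed". Their target is "change in MoCA and costs of dual task in gait performance from baseline to 24 weeks", for enhanced against standard tai ji quan and for enhanced tai ji quan against stretching. The level is an "adjusted significance level of <0.0125 (0.05 / 4 comparisons) and a 98.75% confidence interval (CI".

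The same section promises group means with standard errors at each visit and between-group differences with intervals, and it assigns the primary outcomes to SPSS MIXED. The section on noncompliance and missing data sends ten imputed data sets through the linear mixed model and pools the results. The 48-week analyses reuse this strategy for every outcome except CDR-SB.

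Not stated: a random slope, a residual covariance structure, a robust standard error, the level of the interaction gate, and whether the t tests and intervals are computed on change scores or from the fitted model.

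**The concern.** A random intercept with independent residuals implies equal variances and one common correlation for every pair of visits. The primary contrast uses one particular pair, baseline and 24 weeks, which has the widest gap of the three and the whole intervention in between. If that pair is the least correlated, a model that pools the three correlations understates the variance of the primary change. The confirmatory test would then be anti-conservative and the 98.75% interval too narrow.

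The plan's own CDR-SB growth model, on the same visits plus week 48, allows a slope variance and a separate error variance at each visit. The model named for the co-primary outcomes has no such term.

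**Working it through.** **The plan's own figure.** The documents give no standard error or error rate for the mixed model. The only related figure is the sample size: 267 evaluable participants (89 per arm), a 1.5-point MoCA difference, SD 3.5, two-sided 0.05. With 3.5 read as the SD of change, the noncentrality is (1.5/3.5) × √(89/2) = 2.859, and power is Φ(2.859 − 1.960) = 81.6%. Then 267/0.85 = 314.1, rounded up to 315. Both stated figures reproduce.

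**Formula.** With complete, balanced data, a random-intercept model with independent residuals estimates the variance of any change as the mean of the three pairwise change variances. With equal variances σ²:

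- model: 2σ²(1 − ρ̄), where ρ̄ is the mean of the three correlations
- truth: 2σ²(1 − ρ(0,24))
- SE ratio = √[(1 − ρ̄)/(1 − ρ(0,24))]
- true level = 2[1 − Φ(2.498 × SE ratio)], where 2.498 is the two-sided 0.0125 critical value

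**Inputs.** ρ(0,24) = 0.7 is the pre/post value in the power section. The other correlations are assumptions. For AR(1) decay, ρ(0,16) = 0.7^(16/24) and ρ(16,24) = 0.7^(8/24). For milder decay, the exponents are the square roots of those fractions.

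| Pattern | ρ(0,16) | ρ(0,24) | ρ(16,24) | ρ̄ | SE ratio | True level |
|---|---|---|---|---|---|---|
| Equal | 0.70 | 0.70 | 0.70 | 0.700 | 1.000 | 0.0125 |
| Small departure | 0.71 | 0.70 | 0.72 | 0.710 | 0.983 | 0.014 |
| Milder decay | 0.747 | 0.700 | 0.814 | 0.754 | 0.906 | 0.024 |
| AR(1) in weeks | 0.788 | 0.700 | 0.888 | 0.792 | 0.832 | 0.038 |
| Not decaying | 0.65 | 0.70 | 0.70 | 0.683 | 1.027 | 0.010 |

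For AR(1), √(0.208/0.300) = 0.832, and the 98.75% interval covers 96.2%. As ρ(0,24) moves from 0.5 to 0.8, the AR(1) ratio runs from 0.847 to 0.827 (level 0.034 to 0.039), and the milder ratio from 0.917 to 0.901 (0.022 to 0.024).

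**Simulation.** 40,000 null trials per pattern, three arms of 89, complete data, SD 3.5 at each visit, ρ(0,24) = 0.7. Here 3.5 is read as the SD at one visit; the ratios and levels do not depend on that choice.

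| Quantity | Equal | Milder decay | AR(1) |
|---|---|---|---|
| Model SE / true SE | 0.406 / 0.405 | 0.368 / 0.409 | 0.338 / 0.407 |
| Model contrast at 0.0125, ungated | 0.012 | 0.024 | 0.039 |
| Model contrast, also passing a 0.05 gate | 0.008 | 0.016 | 0.025 |
| t test on change scores at 0.0125 | 0.012 | 0.012 | 0.013 |
| Interaction test at 0.05 | 0.052 | 0.055 | 0.064 |

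The 0.05 gate is an assumption. With the interaction tested at 0.0125, its simulated levels are 0.014, 0.015 and 0.023.

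**Role of spacing.** With visits at 0, 12 and 24 weeks and AR(1) decay, the ratio is 0.834 against 0.832. Unequal spacing is not the cause; decay is.

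**48 weeks.** If the same model takes all four visits under the same AR(1) decay, ρ(0,48) = 0.7² = 0.49 and ρ̄ = 0.698. The ratio is √(0.302/0.51) = 0.77, and 0.0125 becomes 0.055.

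**The case against.** The strongest reply is that the plan names its test. The pairwise comparisons are independent t tests, and a two-sample t test on change scores takes its standard error from the observed changes. The mixed-model covariance then does not enter, and the level stays at 0.012 to 0.013 in every simulated pattern. This stands as far as it goes. But the plan does not say the t tests are on change scores. It also assigns the primary outcomes to SPSS MIXED, promises means and differences with standard errors and intervals, and pools the linear mixed model over imputations. Model-based contrasts and intervals therefore remain a fair reading.

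A second reply is that naming random intercepts does not exclude a structured residual. The text also speaks of repeated measures, and the Synopsis describes the model without any random intercept. That stands too: independent residuals are the natural reading, not a stated fact.

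Third, decay is not documented. The only correlation given is a single pre/post value, and the error vanishes or reverses under other patterns. This also stands, which is why the result is given as a range.

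Fourth, the interaction gate reduces the inflation: 0.024 and 0.039 become 0.016 and 0.025 with a gate at 0.05. Some inflation remains.

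**Conclusion.** This is a gap in specification with a conditional consequence. The residual covariance and the source of the standard error for the 24-week contrasts are not stated. If the contrasts come from a random-intercept model with independent residuals, and if correlation decays with time, the standard error is about 2% to 17% too small. An ungated contrast at nominal 0.0125 then has a true level of about 0.014 to 0.039. These figures assume equal variances and complete data, and they ignore between-imputation variance. There is no error under equal correlations, slight conservatism under some other patterns, and little effect on the Group by Time test at 0.05. The 48-week analysis is more exposed.

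A reader might infer that the plan fixes a wrong standard error for its confirmatory tests, or that the unequal visit spacing produces it. The documents support neither. They leave open a change-score t test that is immune, they do not say the residuals are independent, and equal spacing gives almost the same result. The point is still worth settling, because one reading of the plan protects the primary error rate and the other may not, and the remedy costs almost nothing.

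**What to change.** In SPSS MIXED, replace the random intercept with a REPEATED time effect and unstructured covariance, with Satterthwaite degrees of freedom. Take the 24-week between-arm contrasts, their tests and the 98.75% intervals from that model in each imputed data set, and pool them. Say that this replaces the separate independent t tests, so that p-values and intervals share one source. Use the same structure for the 48-week analysis. Name a heterogeneous structure, such as heterogeneous Toeplitz, as the fallback if the model does not converge. If the sponsor prefers change-score t tests, stating that both tests and intervals use change scores would also close the gap.

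The cost is a few lines of SAP text and code. For three visits, unstructured covariance has 3 variances + 3 covariances = 6 parameters against 2 for compound symmetry, so four more to estimate, which 315 participants (or 267 evaluable) support easily.
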